## Objectives

To evaluate the effects of umbilical cord clamping at different time after cesarean section on the health outcomes of offspring hemoglobin, maternal blood loss, as well as children's growth and development.

## Primary outcomes

The neonatal hemoglobin and the change in maternal hemoglobin.

## Secondary outcomes

The incidence rate of neonatal anemia and jaundice, Apgar score, the incidence rate of neonatal intensive care unit (NICU) admission, placental weight, maternal hemoglobin after the cesarean, estimated maternal blood loss, the incidence rate of maternal blood transfusion.

## Exploratory secondary outcomes

The children's hemoglobin, anemia, growth, and development.

## Statistical Analysis

The primary analysis will be conducted following the intention-to-treat principle. All tests will be two-sided with alpha set at 0.05. No adjustment will be made for multiple testing for multiple outcomes.

Baseline characteristics and outcomes will be summarized using appropriate descriptive statistics: mean (standard deviation) or median (P25~P75) for continuous variables, counts (%) for categorical variables. For continuous variables, Analysis of Variance (ANOVA) or Kruskal-Wallis test will be used to examine the differences among the three intervention groups and the control group as appropriate. For categorical variables,  $\chi^2$  or Fisher exact test will be carried out as appropriate.

Given an anticipated low rate of loss-to-follow up concerning the primary outcomes, the primary analyses will be conducted following a complete case strategy. Specifically, the neonatal hemoglobin and the change in maternal hemoglobin will be analyzed using mixed linear regression model (with necessary transformation for better normality) or mixed median regression model, where study center will be modelled as

a random effect. Potential confounding factors that differ among groups at baseline will be adjusted. Non-inferiority test will be employed with respect to the effect of delayed cord clamping on the change in maternal hemoglobin, in which the margin of non-inferiority is set at 0.87 g/dL, an expected clinically significant difference of the change in maternal hemoglobin. Non-inferiority would be concluded if the lower limit of the confidence interval was greater than -0.87 g/dL. If significant differences are observed in neonatal hemoglobin between groups, appropriate methods (such as trend test) will be used to further explore the association between different time of umbilical cord clamping and neonatal hemoglobin level. Center-stratified analysis will be carried out with generalized linear regression model to determine whether the effect on primary outcomes varies across centers.

Secondary analyses will also be conducted only among complete cases. Mixed linear regression model (with necessary transformation for better normality) or mixed median regression model will be used to evaluate the effects of delayed cord clamping on the Apgar score, placental weight, maternal hemoglobin after the cesarean, and estimated maternal blood loss. Mixed logistic regression model will be fitted to assess the effects on the incidence rate of neonatal anemia, neonatal jaundice, neonatal intensive care unit (NICU) admission, and maternal blood transfusion. Center effects will be modeled by including a random effect. Potential confounding factors that differ among groups at baseline will be adjusted.

Multiple imputation method will be applied to deal with missing values before the analysis of exploratory secondary outcomes, if needed, and the results based on imputed data will be compared with those based on complete cases. Mixed linear regression model (with necessary transformation for better normality), mixed median regression model and mixed logistic regression model will be constructed as appropriate to estimate the effect on follow-up outcomes of children. These outcomes primarily include the hemoglobin and anemia at 6, 12, 18 months, the Z-score of length and weight at 3, 6, 12, 18 months, and the results of Denver Developmental Screening Test (DDST) at 3, 6, 12, 18 months. Random effects of centers and months of follow up will be set in models for the dependencies among observations nested within individuals and centers. Length and weight at birth are the pre-specified covariates for the models of follow-up length and weight, respectively. Baby sex is the pre-specified covariate for the model of the DDST result. Other confounding factors that differ among groups at baseline will be adjusted.

Sensitivity analysis will be performed on the basis of per-protocol dataset to confirm the robustness of the main result of two primary outcomes. Participants will be considered as compliant with the protocol if the time of cord clamping is as follows:

Arms	Anticipated procedure	Permissible time range
Control group	Immediately clamp	< 15s
Experimental group1	Clamp at 30s after delivery	≥15s and < 45s
Experimental group2	Clamp at 60s after delivery	≥45s and < 75s
Experimental group3	Clamp at 90s after delivery	≥75s and < 105s

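### Does the silence on arm contrasts and on error control across three delayed arms require a change to the primary analysis?

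*SAP*

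**What the plan says.** The SAP names two primary outcomes: "The neonatal hemoglobin and the change in maternal hemoglobin". Its objective is to study "umbilical cord clamping at different time after cesarean section". The compliance table at the end of Statistical Analysis lists an immediate-clamping control and three separate delayed arms, the last being "Clamp at 90s after delivery".

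On error control, Statistical Analysis says "All tests will be two-sided with alpha set at 0.05. No adjustment will be made for multiple testing for multiple outcomes". It gives no rule for several arms.

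On comparisons it offers three things:

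- ANOVA or Kruskal-Wallis across all four groups, in the paragraph on summarising baseline data and outcomes.
- A mixed linear or mixed median model for the two primaries, with centre as a random effect and no contrast named.
- A follow-up exploration, such as a trend test, under the condition "If significant differences are observed in neonatal hemoglobin between groups".

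For the mother, "Non-inferiority test will be employed with respect to the effect of delayed cord clamping on the change in maternal hemoglobin", and "Non-inferiority would be concluded if the lower limit of the confidence interval was greater than -0.87 g/dL". The interval is in the singular and no arm is named.

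**The concern.** With group as a four-level factor, the primary model gives three comparisons with control, but the decision rule mentions one interval. On its face the text could mean each arm against control, an overall test followed by the arms, one pooled delayed group, or a rule that all arms must pass. These readings differ in error rate and in what may be said about a given clamping time.

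The trial is about the timing of clamping, so a conclusion about one delay is its main product. Three unadjusted looks at one control could let chance in one arm be reported as a benefit for the newborn or as safety for the mother. A pooled contrast could declare delayed clamping non-inferior while the longest delay lies at the margin. If nothing fixes the reading, it could be settled after the data are seen.

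**Working it through.** The SAP gives no sample size, power, standard deviation or allocation ratio, so it has no figure of its own to reproduce. What can be computed is the cost of each reading.

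**Inputs.** From the SAP: alpha 0.05 two-sided, three delayed arms, one control, margin 0.87 g/dL. Assumed: equal arms and normal statistics. A contrast then has variance 2s²/n and two contrasts share the control's s²/n, so their correlation is 1/2.

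**Each arm against control, unadjusted, no arm effective.**

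- Independent tests would give 1 - 0.95³ = 14.3%.
- With a shared control, the two-sided error is 1 - ∫ φ(x)[Φ((c + √ρ x)/√(1-ρ)) - Φ((-c + √ρ x)/√(1-ρ))]³ dx. With c = 1.96 and ρ = 0.5 this is 12.5%.
- In the favourable direction only, it is 1 - ∫ φ(x)[Φ((c + √ρ x)/√(1-ρ))]³ dx = 6.3%. It runs from 5.6% to 6.8% for correlations from 0.67 to 0.33.

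**Overall 3-df test first, then the arms** (simulation, 2 million draws). The error is 4.0% if no arm works (2.0% favourable). Once one arm clearly works, it is 9.1% over the other two (4.5% favourable).

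**Maternal non-inferiority.** "All tests will be two-sided with alpha set at 0.05" points to a 95% interval, so each lower limit is a one-sided 2.5% test. The chance of at least one false claim is:

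| Arms exactly at -0.87 g/dL | Any-arm error |
|---|---|
| one | 2.5% |
| two | 4.5% |
| three | 6.3% |

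If maternal loss rises with delay, the longest delay reaches the margin first, and the one-arm row applies.

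**Pooled contrast.** Its standard error is √(4/3)/√2 = 0.816 of the per-arm value. Suppose 80% per-arm power, so that margin/SE = 1.96 + 0.84 = 2.80, and put the 90 s arm at -0.87.

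- Other arms at 0: the pooled effect is -0.87/3 = -0.29, which leaves two thirds of the margin. P(Z > 1.96 - 0.667 × 2.80/0.816) = P(Z > -0.33) = 63%.
- Linear in time: the effects are -0.29, -0.58 and -0.87, with mean -0.58. P(Z > 1.96 - 0.333 × 2.80/0.816) = P(Z > 0.82) = 21%.

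**Price of formal control.** Step-down Dunnett uses critical values 2.35, 2.21 and 1.96. From 80% unadjusted, per-arm power on one outcome becomes:

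| Scenario | Step-down Dunnett | Holm |
|---|---|---|
| all arms work equally | 74% | 73% |
| 90 s arm, linear response | 69% | 67% |
| only one arm works | 68% | 66% |

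The Dunnett loss is 80 - 74 = 6 to 80 - 68 = 12 points. Restoring 80% in the last scenario would take about 29% more patients. A rule that all arms must be non-inferior needs no adjustment but has 61% power.

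**Which reading the text supports.** Pooling is mentioned nowhere. The arms are kept apart in the group comparison and in the compliance table. The generic reference to delayed clamping in the non-inferiority sentence recurs in the paragraph on secondary outcomes, where it serves as shorthand for the intervention. The 63% and 21% therefore describe a reading with little support. The four-group test and the conditional trend test lend some support to an overall test followed by exploration. A model with a group factor gives each arm against control directly.

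**The case for a change.** The strongest case for a change is that the non-inferiority rule is a pass/fail rule and cannot be carried out literally: three intervals will exist and the rule speaks of one. The four-group ANOVA does not cure this. It stands in a descriptive paragraph, is not declared a gate, and cannot settle non-inferiority. Even as a gate it leaves 9.1% over two ineffective arms when the third clearly works. The trend test is exploratory and covers only the neonatal outcome. One may hold that separate clamping times are separate questions that need no adjustment, but the SAP does not say so.

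Much of this stands. The contrast, the any-arm or all-arms rule and the policy across arms are unwritten, and the arithmetic is right.

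It does not show a wrong analysis. The sentence that waives adjustment is a disclosed decision about outcomes and is not mistaken in itself. The 6.3% for non-inferiority needs all three delays exactly at the margin, and the pooled figures rest on an assumed power and a reading that the text hardly supports. A later choice of reading is possible but not shown, since the protocol, which is not at hand, may fix the contrasts. Nor is step-down Dunnett the only remedy: Holm, a fixed sequence, an all-arms rule or an open policy of no adjustment per arm would each be defensible.

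**Conclusion.** The concern is accurate about what is unwritten but calls for no change. An analyst would ordinarily fit group as a factor, give each delayed arm's difference from control with its 95% interval, and hold each maternal lower limit against -0.87 g/dL. Every arm then appears in the report and each arm's claim keeps its own error: 5% two-sided for the newborn, 2.5% one-sided for non-inferiority. A reader can apply a stricter threshold to the three results.

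Under that reading, the error over the set of arms is 12.5% two-sided (6.3% favouring delay) for neonatal haemoglobin, and 2.5% to 6.3% for maternal non-inferiority, depending on how many arms lie at the margin. Removing it by step-down Dunnett would cost about 6 to 12 points of per-arm power. Whether that is worth paying in a trial that tests each question at 0.05 is a matter of judgement on which statisticians differ.

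These figures assume equal arms and normal statistics. The power figures also assume 80% unadjusted power for the largest contrast, because the SAP states no sample size.

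### The maternal non-inferiority limit is fixed in g/dL, but the plan allows models whose limit is not in g/dL or whose estimand is a median

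*SAP*

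**What the plan says.** The SAP's Primary outcomes section names two: "The neonatal hemoglobin and the change in maternal hemoglobin". One paragraph of Statistical Analysis covers both. They are to be "analyzed using mixed linear regression model (with necessary transformation for better normality) or mixed median regression model", with center as a random effect. For the maternal outcome, "the margin of non-inferiority is set at 0.87 g/dL, an expected clinically significant difference of the change in maternal hemoglobin", and the decision rule follows: "Non-inferiority would be concluded if the lower limit of the confidence interval was greater than -0.87 g/dL".

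The only criterion for leaving the plain linear model is "with necessary transformation for better normality". No transformation, test or threshold is named, and nothing says when the median model replaces the linear one. The rule does not say which model supplies the interval. The later paragraphs of the section repeat the model wording for other outcomes and do not settle the point.

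Two facts set the scope. There are three delayed arms and a control ("examine the differences among the three intervention groups and the control group as appropriate"), so the rule may be applied more than once. Neonatal hemoglobin is tested for a difference ("If significant differences are observed in neonatal hemoglobin between groups, appropriate methods (such as trend test) will be used") and has no g/dL bound, so the conflict concerns the maternal outcome only.

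**The concern.** A non-inferiority margin has meaning only for a stated quantity on a stated scale. Here the threshold is fixed in g/dL, while the model producing the number to be compared with it is left open among three options. If a transformation is used, the stated rule cannot be applied without a conversion that the SAP does not give. If the median model is used, the comparison can be made, but it answers a different question.

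Choosing a model to improve normality requires looking at the distribution. The null hypothesis behind a primary non-inferiority claim would thus be settled after data are available, and the choice carries into each delayed arm's comparison with control.

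**Working it through.** The SAP states no SD, sample size or named transformation, so it has no figure to reproduce. The only inputs from it are the margin (0.87 g/dL), the rule (lower limit above -0.87 g/dL), the permitted models, and two-sided alpha of 0.05, which implies a 95% CI. Everything else below is assumed.

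**1. The rule against each permitted model**

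| Model | Unit of the limit | Quantity estimated | Rule usable as written? |
|---|---|---|---|
| Linear, untransformed | g/dL | mean difference | yes |
| Linear, transformed | transformed units | difference on that scale | no; conversion not given |
| Median | g/dL | median difference | only if the margin is meant as a median difference; not stated |

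**2. Transformed model.** A change score can be zero or of either sign, so a log needs a shift c. Let x be the control change (negative for a fall) and analyse -log(c - x). The coefficient worth -0.87 g/dL at x = -1.0 is b = -log[(c + 1 + 0.87)/(c + 1)]. Its value in g/dL at another x is -(c - x)(exp(-b) - 1).

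- c = 3: exp(-b) = 4.87/4 = 1.2175. At x = -0.5: -3.5 × 0.2175 = -0.76. At -1.5: -4.5 × 0.2175 = -0.98. At 0 and -2.0: -0.65 and -1.09.
- c = 5: exp(-b) = 6.87/6 = 1.145, giving -0.80 at -0.5 and -0.94 at -1.5.
- Square root, c = 3: the shift is √4.87 - √4 = 0.2068. At x = -0.5: -[(1.8708 + 0.2068)² - 3.5] = -0.82. At -1.5: -[(2.1213 + 0.2068)² - 4.5] = -0.92.

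One coefficient therefore has no single g/dL equivalent, and the spread depends on the transformation and shift chosen.

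**3. Median model.** Let the control change be normal with SD s, and the delayed-arm change the same minus an extra fall averaging 0.87. The true mean difference is -0.87 throughout.

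| Extra fall | s = 0.7 | s = 1.0 | s = 1.3 |
|---|---|---|---|
| Equal for every woman | -0.87 | -0.87 | -0.87 |
| Exponential | -0.74 | -0.78 | -0.80 |
| Gamma, shape 2 | -0.82 | -0.84 | -0.85 |
| 60% of women lose 1.45 each (0.87/0.6) | -0.93 | -0.90 | -0.89 |

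Entries are median differences in g/dL. The last row solves 0.4Φ(m/s) + 0.6Φ((m + 1.45)/s) = 0.5 for m. Conversely, under the exponential fall, a median difference of exactly -0.87 goes with mean differences of -1.06, -0.99 and -0.96.

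A second illustration assumes a lognormal fall with equal log-SD σ in both arms. The median difference is then 0.87 × exp(-σ²/2) in size: 0.83, 0.77 and 0.63 for σ = 0.3, 0.5 and 0.8.

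**4. What an untransformed mean rule would give**

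- Power at no true difference, Φ(0.87/(SD√(2/n)) - 1.96): with n = 50 per arm and SD 1.0, Φ(4.35 - 1.96) = 99%; with SD 1.3, 92%. With n = 100 and SD up to 1.3, above 99%.
- 95% CI width, SD 1.0 and n = 100 per arm: 2 × 1.96 × √(2/100) = 0.55 g/dL for the mean. Dividing by 2f(median), where f is the standardized gamma density, gives 0.69, 0.66 and 0.55 for the median at skewness 0.5, 1 and 2.
- Simulation at a true mean difference of -0.87 (10,000 comparisons per scenario; 50 to 200 women per arm; six centers as fixed terms; skewed residuals; HC3 standard errors): non-inferiority was concluded 2.2-2.8% of the time. A simpler simulation without centers (4,000 runs) gave 2.7% and 2.9% at 100 and 200 per arm. The nominal rate is 2.5%.

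**The case against.** The strongest reply is that the model sentence is general wording for both primary outcomes, and the specific g/dL rule that follows should override it. That is a sensible intention, but the text does not say so: the paragraph applies the transformation option to this outcome by name and never withdraws it.

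Other objections limit the point without removing it:

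- The log, the square root and the shifts are assumptions, and milder choices shrink the spread. This stands, so the figures are illustrations only.
- The median limit remains in g/dL, the gaps are mostly modest, they vanish under an equal shift and their direction is not fixed. All true. No bias towards a false claim is shown.
- If the true effect is far from the margin, mean and median limits would usually both clear it. True; the choice matters mainly near the margin, and nothing in the SAP says where the effect lies.
- Normality might be checked on pooled or blinded data. The SAP does not say. Blinding would reduce the scope for a choice driven by results, but would not put a transformed limit back into g/dL or define the estimand.
- The protocol, which is not at hand, may explain whether the margin was derived for a mean or a median. That could answer one part, but not the missing analysis scale in a rule that the SAP itself states.
- The simulation shows only that the mean rule works for the mean, and uses fixed rather than random center terms. Agreed; it supports the remedy and does not estimate any error rate of the present plan.

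**Conclusion.** The point holds and the text is wrong as written: one of the permitted analyses makes the stated rule inapplicable, and another changes the hypothesis without saying so. The defect is conditional. If the untransformed linear model is used, the rule works. If every woman's change shifts equally, the mean and median differences coincide.

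Under the assumed scenarios, the g/dL value of one transformed coefficient varies by about 0.05 to 0.11 g/dL for each 0.5 g/dL move in the reference level. The median difference departs from a mean difference of -0.87 by 0 to 0.13 g/dL in the normal-based scenarios, in either direction, and by up to 0.24 g/dL (0.87 - 0.63) in the most skewed lognormal case. These figures show that the quantities can differ; they are not error rates. Because this is a primary decision and the cure is a matter of wording, it should be fixed, though the practical consequence is uncertain.

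**What to change.** State that each maternal non-inferiority decision (each delayed arm against control) rests on the adjusted difference in mean change in hemoglobin, untransformed and in g/dL, from the mixed linear model with a two-sided 95% CI. Give the sign convention; the rule's sign implies post minus pre and delayed minus control. If residuals are not normal, use robust or bootstrap standard errors instead of a transformation. Keep transformed and median models as sensitivity analyses that carry no non-inferiority decision.

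Pre-specifying the margin as a median difference would also close the gap, provided the SAP says so and removes the other models from the decision. The transformation wording can stay for neonatal hemoglobin.

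The cost is one or two sentences and no new data. Under strong skewness the interval may be slightly wider than with a well-chosen transformation. In the cases calculated above it is no wider than the median model's, and power remains high under the assumed sizes.

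### The child follow-up models name random effects for center and month only, so the correlation among one child's visits, which the sentence says they address, is not modelled

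*SAP*

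**What the plan says.** The passage concerned is the paragraph on exploratory secondary outcomes in the SAP's Statistical Analysis section. Mixed linear, median and logistic models "will be constructed as appropriate to estimate the effect on follow-up outcomes of children".

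The visit schedule follows: "These outcomes primarily include the hemoglobin and anemia at 6, 12, 18 months", and "the Z-score of length and weight at 3, 6, 12, 18 months". The DDST is also scheduled at 3, 6, 12 and 18 months. Each child thus contributes up to 3 values for hemoglobin and anemia, and up to 4 for length, weight and DDST.

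The random-effects structure is fixed in one sentence: "Random effects of centers and months of follow up will be set in models for the dependencies among observations nested within individuals and centers".

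Two other statements bear on the size of the problem. On covariates: "Length and weight at birth are the pre-specified covariates for the models of follow-up length and weight, respectively". On testing: "All tests will be two-sided with alpha set at 0.05", with no multiplicity adjustment across outcomes.

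**The concern.** The sentence names two random effects and two levels of dependence, and the lists do not match. Its purpose includes dependence within individuals, but the individual receives no term.

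Arm is constant within a child. When one arm effect is averaged over visits, positive correlation among a child's visits means that 3 or 4 values carry less information than 3 or 4 independent ones. A model that leaves this out counts visits as if they came from different children (apart from shared center and month effects). It then reports a standard error that is too small and an interval that is too narrow.

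What is at stake is inference on child hemoglobin, anemia, growth and development. These outcomes are labelled exploratory, but growth and development are part of the SAP's stated objective.

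**Working it through.** **1. What each named term does.** Compare two visits of one child with two visits, at the same two ages, of two different children in the same center.

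| Term | Same child | Different children, same center |
|---|---|---|
| Center effect | shared | shared |
| Month effect common to all children | differs by visit | differs by visit |
| Child effect | not named | not named |

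Under the named terms the two pairs have the same modelled correlation. Within-child correlation therefore goes unmodelled.

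**2. Inputs.** From the SAP: m = 3 visits (hemoglobin, anemia) or m = 4 (length, weight, DDST), and two-sided alpha of 0.05. The SAP gives no within-child correlation (ICC) and no standard error or error rate for these models, so there is no figure of its own to reproduce. Assumed: ICC of 0.3 to 0.7 after covariates, equal for all pairs of visits, and one arm compared with control.

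**3. Linear model as written, arm effect averaged over visits.** The true variance exceeds the reported variance by DE = 1 + (m − 1) × ICC. The true level is 2 × [1 − Φ(1.96/√DE)], and the coverage of a nominal 95% interval is 1 minus that.

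| m | ICC | DE | True SE / reported SE | True level | Coverage |
|---|---|---|---|---|---|
| 3 | 0.3 | 1.6 | 1.26 | 12.1% | 87.9% |
| 3 | 0.5 | 2.0 | 1.41 | 16.6% | 83.4% |
| 3 | 0.7 | 2.4 | 1.55 | 20.6% | 79.4% |
| 4 | 0.3 | 1.9 | 1.38 | 15.5% | 84.5% |
| 4 | 0.5 | 2.5 | 1.58 | 21.5% | 78.5% |
| 4 | 0.7 | 3.1 | 1.76 | 26.6% | 73.4% |

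Simulation agrees. With center and month both random (REML; assumed 4 arms of 100 and 5 unequal centers; 2,000 runs per cell), the levels at ICC 0.3/0.5/0.7 were 13.4/17.8/20.2% for 3 visits and 15.7/22.7/26.6% for 4. At ICC 0 they were 5.1% and 4.7%, so the excess comes from the within-child correlation and not from the random month term.

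**4. A more generous reading: a month slope varying by child, without a child intercept.** This ties a child's visits together, but by an amount proportional to the product of the two ages. Fitting that structure to a constant correlation gives limiting levels of 8.3/11.3/15.5% (3 visits) and 11.7/16.8/22.4% (4 visits) at ICC 0.3/0.5/0.7. The inflation is only partly removed.

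**5. Length and weight, adjusted for birth size.** If birth size correlates r with later size (assumed 0.3 to 0.5), a raw ICC becomes (ICC − r²)/(1 − r²). With 4 visits:

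| Raw ICC | Residual ICC, r = 0.3 | Level | Residual ICC, r = 0.5 | Level |
|---|---|---|---|---|
| 0.7 | 0.67 | 26% | 0.60 | 24% |
| 0.5 | 0.45 | 20% | 0.33 | 17% |
| 0.3 | 0.23 | 13% | 0.07 | 7% |

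**6. Logistic and median models (less certain).**
- Logistic models with random center and month were fitted to simulated data (1,000 runs per cell; assumed prevalence 10–30% and latent correlation 0.3–0.7). They gave about 8–18% for anemia (3 visits) and 10–19% for a yes/no DDST result (4 visits).
- For the median model, putting (2/π) × arcsin(ICC) in place of ICC in DE gives 9.6/12.9/16.4% (3 visits) and 11.9/16.6/21.3% (4 visits). This applies if the standard errors treat visits as independent, and it was not checked by fitting.

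**7. Arm effect at one age.** Each child then contributes one value to the contrast, so there is nothing to inflate. Simulation gave 4.7–5.7%.

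**8. With a child intercept, random center and fixed month.** The simulated level was 4.8/4.7/4.8% (3 visits) and 4.5/5.3/5.5% (4 visits) at ICC 0.3/0.5/0.7, in line with the nominal 5%.

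**The case against.** The strongest reply is that the sentence states its aim, "for the dependencies among observations nested within individuals and centers", and so should be read as intending child-level dependence. If month effects vary by child, with month categorical and freely correlated within a child, the within-child covariance is unstructured and the level returns to 5.0%. That reading uses only words found in the sentence. It does, however, need a grouping and a covariance that the SAP does not state: independent month effects within child would not do, and a month slope alone falls short (step 4). The stated aim shows what was wanted; the terms listed do not deliver it.

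A second reply is that the harm is conditional. It needs the literal reading, an arm effect averaged over visits (which the SAP never specifies) and an assumed correlation. For length and weight the pre-specified birth-size adjustment could bring the level down to about 7%. All of this stands and limits the claim. It does not remove it, because an averaged effect is a natural output of a joint model of all visits.

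Third, making month a fixed factor is partly preference, since random month alone did no harm at ICC 0. That is fair. The essential repair is the child-level term; with only 3 or 4 planned levels, a fixed factor is simply the better choice for month.

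Finally, only exploratory outcomes are affected. This too is correct and bounds the importance of the point.

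**Conclusion.** The concern holds. The SAP does specify a random-effects structure, and that structure fails the purpose given for it; this is not detail left to the protocol.

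The size depends on three conditions: the model is fitted as written, the reported arm effect is averaged over visits, and the within-child correlation after covariates is 0.3 to 0.7. The linear model then has a true level of about 12–21% (3 visits) or 16–27% (4 visits), and nominal 95% intervals cover about 79–88% or 73–84%. The linear closed-form result is well supported by simulation. The logistic figures also rest on assumed prevalence, and the median figures on a formula alone.

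The two primary outcomes, the non-inferiority test and the other secondary outcomes have no stated repeated visits and are not affected. The point should be fixed, but it does not threaten the trial's main conclusions. Confidence is medium, because the wording is terse and the form of the reported effect is not stated.

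**What to change.** Replace the random-effects sentence with wording such as:

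> The linear, median and logistic follow-up models will each include a random effect for center and, in addition, a random intercept for child (or an explicit within-child covariance). Month of follow-up will be a fixed categorical factor.

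Also state whether the reported arm effect is averaged over visits or given by age. A group-by-month interaction with effects by age may be added, but is not needed to cure the defect.

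The cost is SAP wording and model code. No new data, visits or participants are required.

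### The child follow-up models enter visit month only as a random effect and specify no arm-by-month term, so as described they give one age-averaged arm effect and would not show an effect that changes with age.

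*SAP*

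**What the plan says.** The SAP's Objectives section names offspring hemoglobin and maternal blood loss, "as well as children's growth and development". The children's outcomes are classed as exploratory secondary. In Statistical Analysis they are listed by age:

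- "the hemoglobin and anemia at 6, 12, 18 months"
- "the Z-score of length and weight at 3, 6, 12, 18 months"
- "the results of Denver Developmental Screening Test (DDST) at 3, 6, 12, 18 months"

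Mixed linear, median or logistic models "will be constructed as appropriate to estimate the effect on follow-up outcomes of children". On repeated visits the SAP says: "Random effects of centers and months of follow up will be set in models". The stated purpose is to handle dependence between observations within children and within centers.

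The other model terms named are birth length or birth weight for the growth models, baby sex for the DDST model, and baseline factors on which the groups differ. The SAP mentions no fixed effect of month, arm-by-month term or visit-specific arm contrast. It sets alpha at 0.05 two-sided and makes no multiplicity adjustment.

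**The concern.** The visit ages were chosen by design and have an order. They are not a sample from a population of months, and a variance estimated from three or four levels is unstable. More importantly, a random month term absorbs differences in mean level between visits but leaves a single coefficient for each delayed arm against control. That coefficient is an average over the visits. It describes the effect at every age only if the effect is the same at every age, and the SAP gives no ground for assuming so.

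At stake is what the follow-up can report. Children are seen repeatedly up to 18 months, yet the model as described would not say at which age a difference is present. An effect confined to one visit would be diluted by the others, and effects of opposite sign at different ages could cancel.

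**Working it through.** **What the SAP supplies.** Visit ages (three for hemoglobin and anemia; four for length Z-score, weight Z-score and DDST), four arms, alpha 0.05 two-sided. It states no sample size, power, SD, effect size or within-child correlation for these outcomes, so there is no figure to reproduce.

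**Assumptions for the illustration.** One delayed arm against control, a continuous outcome with equal variance at T = 3 balanced visits, equal correlation rho between a child's visits (0.3 or 0.5), and within-child correlation properly handled. The effect at 6 months would have 80% power if tested alone, so z6 = 1.96 + 0.84 = 2.80.

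**Formula.** Without an interaction, the arm coefficient is the mean of the visit effects. Relative to a single visit, its standard error is multiplied by sqrt((1 + 2 rho)/3):

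- rho = 0.3: sqrt(1.6/3) = 0.730
- rho = 0.5: sqrt(2.0/3) = 0.816

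Pooled z = 2.80 × (mean relative effect) / multiplier. Power is the probability that a normal variable with that mean lies beyond ±1.96.

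| Relative effect at 6, 12, 18 months | Mean | z, rho 0.3 | Power | z, rho 0.5 | Power |
|---|---|---|---|---|---|
| 1, 0, 0 | 1/3 | 1.28 | 25% | 1.14 | 21% |
| 1, 0.5, 0 | 1/2 | 1.92 | 48% | 1.71 | 40% |
| 1, 1, 1 | 1 | 3.83 | 97% | 3.43 | 93% |

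The last row matters as much as the first: with a constant effect, pooling beats the 80% of a single visit.

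**What an interaction would add.** Take SD 1, n = 200 per arm (assumed), rho = 0.5, and effects of 0.3, 0, 0 SD.

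- Pooled effect: 0.3/3 = 0.10. SE = sqrt((2/200) × (1 + 2 × 0.5)/3) = 0.0816; z = 1.22; power 23%.
- First visit alone: z = 0.3/sqrt(2/200) = 3.0; power 85%.
- Arm-by-month test (two arms, 2 df): noncentrality = (n/2) × sum of squared deviations from the mean effect / (1 − rho) = 100 × (0.04 + 0.01 + 0.01)/0.5 = 12; power 88%.

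Across n = 100 to 400 per arm and rho = 0.3 to 0.7, this pattern gives 12% to 49% pooled power, against 44% to 100% for the interaction test. If the effects are 0.3, 0, −0.3 SD, the pooled effect is 0 and its test rejects 5% of the time; at n = 200 the interaction test has at least 99% power. A simulation at n = 200 and rho = 0.5 gave mean pooled estimates of 0.10 and 0.00 for the two patterns, with rejection rates of 24% and 5%.

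**Number of contrasts.** Visit by visit: 3 delayed arms × (3 + 3 + 4 + 4 + 4) = 54. Age-averaged: 3 × 5 = 15. If there were no effect at all, about 0.05 × 54 = 2.7 of the 54 would be nominally significant.

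The power arithmetic fits a linear model. For anemia and any binary DDST result, the averaging takes place on the log-odds scale and the figures are only a guide.

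**The case against.** The strongest reply is that the sentence on random effects concerns dependence between observations, not the mean model. The SAP gives no complete list of fixed effects and leaves the models to be built as appropriate. A random month term, especially a child-level slope on month, is compatible with a fixed interaction. This stands: a reader might infer that the SAP excludes an arm-by-month term, but it only fails to specify one. A random slope would still give no arm effect by age unless an interaction were added.

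A reader might also infer that making month random distorts the arm estimate. With balanced visits and randomised arms, the arm coefficient is nearly the same whether month is fixed or random. The loss of information comes from the unspecified interaction. Length and weight are analysed as Z-scores, which should remove much of the average age course, though an arm difference in Z-score can still vary with age.

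A third tempting step is to treat a fading effect as expected. Nothing in the SAP says so; it is one scenario among several, and under a constant effect the pooled analysis is the better one.

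Separate models at each visit might be meant, since outcomes are listed by age, but a random month effect makes sense only in a pooled model. The ANOVA, Kruskal-Wallis and chi-square comparisons described earlier in Statistical Analysis could be run at each age. The SAP does not say they will be, and they would yield no adjusted estimate of a delayed arm against control.

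**Conclusion.** The point holds as a gap in specification. As described, the pooled child models give one age-averaged effect per comparison and would not show an effect that varies with age. The age average is a legitimate quantity, so this is not an invalid analysis, and the documents do not support saying that a real early effect will be missed. Under the stated assumptions, pooled power ranges from about 21% to 25% if the effect is confined to 6 months to about 93% to 97% if it is constant. Which case applies cannot be known from the SAP. No primary or main secondary conclusion depends on these models. Priority is low to moderate: worth doing because it is cheap and makes use of the planned visits.

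**What to change.** In Statistical Analysis, amend the sentence on random effects in the child follow-up models so that:

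- month of follow-up is a fixed categorical factor with an arm-by-month interaction;
- random effects are kept for clustering only;
- each delayed-arm-versus-control difference is reported with its 95% CI at every visit: months 6, 12 and 18 for hemoglobin and anemia; months 3, 6, 12 and 18 for the two Z-scores and DDST;
- the age-averaged effect is reported alongside;
- the joint arm-by-month test is given once per outcome, and the visit contrasts are labelled exploratory.

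The change takes a few lines of text and a few more model terms, with no new data. The price is lower precision at each visit than for the average when the effect is constant, and 54 unadjusted contrasts in place of 15. The joint tests and the exploratory label are there to keep isolated significant visits from being over-read.
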